This study is designed to assess the efficacy and economics of two NPWT branded devices of wound healing outcomes. It is also designed to assess the effectiveness of negative pressure and negative pressure with continuous irrigation on multiple parameters of wound healing. It is a single-center, open-label, active controlled, parallel-group trial that aims to determine the efficacy of Quantum with simultaneous irrigation in the treatment of diabetic foot ulcers. Specifically, eligible participants will be randomized to receive either PRO negative press therapy with simultaneous irrigation; or PRO negative pressure therapy without irrigation; or KCI Ultra negative pressure therapy. Primary outcomes will include rates of wound healing, time to closure by secondary intention, and recurrence rate.

Study Objectives and Endpoints

Objective 1

- A) To compare clinical outcomes in Wounds treated with Negative Pressure Wound therapy with and without Simultaneous Irrigation.**

H1: The wound healing outcomes of patients treated with NPWT Pro will be non-inferior to the wound healing outcomes of patients treated with NPWT-KCI Ultra

Primary Endpoint:

- Comparison of reduction in wound volume between wounds treated with NPWT PRO and NPWT-KCI Ultra

Secondary Endpoints:

- Comparison of rate of wound healing in wounds treated with NPWT PRO and NPWT-KCI Ultra.

- Comparison of the following variables between the groups: granulation tissue integrity including hypergranulation state, time to close, flap/graft take, dehiscence, and reoccurrence.

B) To compare clinical outcomes in Wounds treated with NPWT PRO with and without Simultaneous Irrigation.

H1: Patients treated with NPWT with irrigation will have higher proportions of wounds that heal and faster wound healing trajectories compare to patients treated with NPWT without irrigation.

H2: Patients treated with Negative Pressure Wound therapy with Irrigation will have fewer wound complications such as infections, amputations, and foot-related hospital admissions.

Primary Endpoints:

- Primary Endpoint: Comparison of reduction in wound volume between wounds treated with NPWT PRO and NPWT PRO with simultaneous irrigation

Secondary Endpoints:

- Comparison of rate of wound healing in wounds treated with NPWT and NPWT with simultaneous irrigation

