- Presents with an existing chronic or traumatic wound, sub-acute or dehisced wound, partial-thickness burn, ulcer (such as a diabetic or pressure ulcer), flap or graft as diagnosed by a qualified and certified medical practitioner (M.D., D.O., or D.P.M)
- Wound presents with full thickness loss of epidermis and dermis
- The presentation of a wound that in the opinion of the investigators will require surgical debridement, and the wound is expected to be a good candidate for NPWT.
- $ABI \geq 0.5$ or toe pressures >30 PVR/mmHg
- Subject is willing and able to abstain from partaking in any other form of treatment for his or her wound during the active treatment phase of this study , other than the study procedures described herein.
- 18 years of age or older

Exclusion Criteria

Subjects that satisfy any one or more of the following exclusive conditions criteria outlined below will be excluded from participation in the clinical study.

- Does not present with an existing chronic or traumatic wound, sub-acute or dehisced wound, partial-thickness burn, ulcer (such as a diabetic or pressure ulcer), flap or graft, or a definitive diagnosis cannot be made, as diagnosed by a qualified and certified medical practitioner (M.D., D.O., or D.P.M)
- Wound does not present with full thickness loss of epidermis and dermis

- ABI<0.5 or toe pressures <30 PVR/mmHg
 - Subject is not willing or is not able or it is not medically prudent for the subject to abstain from partaking in any other form of treatment for his or her wound during the active treatment phase of this study, other than the study procedures described.
 - Subject is unwilling or unable to use the NPWT device at home
 - Active Charcot arthropathy
 - Collagen vascular disease
 - Scleroderma
 - Non-enteric and unexplored fistula
 - Necrotic tissue with eschar present after debridement
 - General skin disorder in the area of the wound such as psoriasis or penicilitis
 - Malnutrition (Defined as BMI < 19)
 - Hypercoagulable state based on documentation in their medical record
 - Acute deep vein thrombosis
 - Current active malignancy in the wound
 - Current melanoma or history of melanoma at the wound
 - Current active or history of invasive squamous cell carcinomas at the wound
 - Sepsis (defined as positive blood culture with leukocytosis) and temperature >101.5 at the time of screening
 - Significant hematologic disorders EXCLUDING anemia
-
- HIV
 - Fever at screening > 101.5
 - Deep X-ray therapy

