Subjects in the KCI arm of this clinical study will receive NPWT alone with the KCI USA, Inc. V.A.C.Via™ NPWT System (K132741) while residing at home. The V.A.C.Via NPWT System is a NPWT powered suction pump that consists of the following components: a sterile dressing system applied to the wound and connected via tubing to a therapy unit that generates negative pressure at the wound; and a sterile, disposable canister that collects wound exudates removed via the negative pressure. The V.A.C.Via™ NPWT System is intended for use as an integrated wound management system in acute, extended and home care settings. It is intended to create an environment that promotes wound healing by secondary or tertiary (delayed primary) intention by preparing the wound bed for closure, reducing edema, promoting granulation tissue formation and perfusion, and by removing exudates and infectious material. It is indicated for patients with chronic, acute, traumatic, subacute and dehisced wounds, partial-thickness burns, ulcers (such as diabetic, pressure or venous insufficiency), flaps and grafts.

Screening and Baseline Procedures

The following is a listing of all of the assessment and safety tools and evaluations to be used in this clinical study. For each study phase, the precise tools to be employed will be specified.

Ulcer History

- Type of wound: chronic or traumatic wound, sub-acute or dehisced wound, partial-thickness burn, ulcer (diabetic, pressure, etc.), flap, graft, other
- Duration since wound onset
- Wound location
- Previous wound history/amputation, if any

Medical Status

- The New York Heart Association (NYHA) Functional Classification System will be used to classify stage of heart failure.
 - The New York Heart Association (NYHA) functional classification system is used to classify the stage of heart failure from Class I to IV (as shown in the table below). This system relates symptoms to everyday activities and the patient's quality of life.

Class	Patient Symptoms
 None	No history of limitations
Class I (Mild)	No limitation of physical activity. Ordinary physical activity does not cause undue fatigue, palpitation, or dyspnea (shortness of breath).
Class II (Mild)	Slight limitation of physical activity. Comfortable at rest, but ordinary physical activity results in fatigue, palpitation, or dyspnea.

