- *Institutional Review Board:* Our Research protocol has been approved by the Institutional Review Board (DHHS IRB Registration No. 00001230). We have not request a waiver of the elements of consent.
- *Informed Consent:* Once a potential study subject is identified, one of the investigators or research staff will discuss the study design, duration of the study, and risks with the patient. We will then provide the subject with a consent form to read. The investigator or study coordinator will be available to answer questions or provide more explanation as requested by the potential study subject and their family. The

emergency department and diabetic foot clinics will be the primary sources for recruitment and screening.

- *Inclusion of Children:* We will not include children in the study because NPWT is not indicated for use in the pediatric population.

Subject Safety and Data Monitoring

All devices used in this comparative effectiveness trial are FDA approved, thus we will not include a formal data safety monitoring board in this study. However, to assure the safety of subjects in this study, an independent review of both aggregate and by treatment group in a blinded fashion each six months, or more often as needed, will be performed by an independent safety monitor, [name], DPM.

Adverse Events

All observed or volunteered adverse events regardless of treatment group or suspected causal relationship to the investigational product(s) will be reported as described in the following sections.

For all adverse events, the investigator must pursue and obtain information adequate both to determine the outcome of the adverse event and to assess whether it meets the criteria for classification as a serious adverse event requiring immediate notification to the Cardinal Health contact. For all adverse events, sufficient information should be obtained by the investigator to determine the causality of the adverse event. The investigator is required to assess causality. For adverse events with a causal relationship to the device, follow-up by the investigator is required until the event or its sequelae resolve or stabilize at a level acceptable to the investigator, and the Cardinal Health contact concurs with that assessment.

Reporting Period

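### The design section names diabetic foot ulcers as the target population, but eligibility enrols a wider set of wounds and no main efficacy comparison is stated to account for wound type

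*Combined protocol and SAP*

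**What the plan says.** **Aim.** Study Groups and Design says that the trial "aims to determine the efficacy of Quantum with simultaneous irrigation in the treatment of diabetic foot ulcers". The rest of that paragraph, and the Objective 1 comparisons, speak of wounds in general.

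**Eligibility.** Under Inclusion Criteria a subject qualifies who "Presents with an existing chronic or traumatic wound, sub-acute or dehisced wound, partial-thickness burn, ulcer (such as a diabetic or pressure ulcer), flap or graft". Three criteria narrow this: "Wound presents with full thickness loss of epidermis and dermis"; a wound that in the investigators' opinion "will require surgical debridement, and the wound is expected to be a good candidate for NPWT"; and an ABI of at least 0.5 or "toe pressures >30 PVR/mmHg". A long exclusion list follows. No criterion asks for diabetes, a foot site or an ulcer.

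**Recruitment.** Under Facilities (informed consent item), the "emergency department and diabetic foot clinics will be the primary sources for recruitment and screening".

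**Baseline data.** Ulcer History records "Type of wound: chronic or traumatic wound, sub-acute or dehisced wound, partial-thickness burn, ulcer (diabetic, pressure, etc.), flap, graft, other", and also wound location. Medical History records diabetes history.

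**Allocation.** Randomization is 1:1:1 by sealed prenumbered envelope for 90 patients. No stratification factor is named.

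**Analysis.** Survival Analyses Models calls Kaplan-Meier with a log-rank test the primary method and names no covariate or stratum. The non-inferiority comparison of PRO with the KCI device, judged within ±10%, names none either. Reduction in wound volume is the primary endpoint of Objectives 1A and 1B, yet no model for it is given. A multivariable Cox model is planned for time to adverse events and for factors behind non-healing or complications. Its worked example contrasts a subject with diabetes and one without.

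**The concern.** The sentence that states the aim and the criteria that decide who enters describe different populations. If the results are written up under the stated aim, an estimate from mixed wounds would be reported as an estimate for diabetic foot ulcers. One stated purpose of the trial is to supply data for powering a larger multicenter study, so a wrongly labelled population could carry over into that study's assumptions.

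The second issue is noise. Wound type may well predict volume reduction and closure. With 30 per arm and no stratification, chance differences in wound type can move both the device contrast and the irrigation contrast. PRO alone is the shared arm in both, so an unusual mix in that arm affects both. Baseline data that could remove this noise are collected, but no main efficacy comparison is stated to use them.

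**Working it through.** **1. Aim against entry criteria**

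| Element of the stated aim | Required for entry? |
|---|---|
| Diabetes | No; the Cox example presupposes subjects without it |
| Foot location | No; the ABI or toe-pressure threshold suggests a lower limb but does not require one |
| Ulcer | No; it is one of several listed wound types |

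The list includes partial-thickness burns while another criterion requires full-thickness loss, so few burns may qualify. The other listed types are not affected.

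**2. The plan's own sample size**

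Inputs from Equations: P1 = 0.60, P2 = 0.90, so P = 0.75; power 0.80.

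n = [z(α/2)·√(2P(1−P)) + z(β)·√(P1(1−P1) + P2(1−P2))]² / (P1−P2)²

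- Two-sided 0.10: (1.645·√0.375 + 0.842·√0.33)² / 0.09 = 24.7. The plan says about 25.
- Two-sided 0.05: (1.960·√0.375 + 0.842·√0.33)² / 0.09 = 31.5. The plan says about 31.

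The figures reproduce. They concern closure, not volume, and they count all enrolled wounds. The closure rates come from hospitalized patients with infected lower-extremity wounds, a group not described as having diabetic foot ulcers.

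**3. What is left for a claim about diabetic foot ulcers alone**

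Let f be the share of subjects with one (not given; assumed). Each arm then has n = 30f.

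Power = Φ{[0.30 − z(α/2)·√(2·0.75·0.25/n)] / √(0.33/n)}

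For n = 30 at two-sided 0.05: (0.30 − 1.960·0.1118)/0.1049 = 0.77, giving 78%. For n = 15: (0.30 − 1.960·0.1581)/0.1483 = −0.07, giving 47%.

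| f | n per arm | Power, α 0.05 | Power, α 0.10 |
|---|---|---|---|
| 100% | 30 | 78% | 87% |
| 80% | 24 | 68% | 79% |
| 60% | 18 | 55% | 68% |
| 50% | 15 | 47% | 61% |

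**4. Chance imbalance between two arms of 30**

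Let X and Y be independent Binomial(30, f) counts of diabetic foot ulcers. A gap of 15 points is 4.5 patients, so it needs |X−Y| ≥ 5. A gap of 20 points needs |X−Y| ≥ 6. Exact probabilities:

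| Assumed f | ≥ 15 points | ≥ 20 points |
|---|---|---|
| 50% | 24.5% | 15.5% |
| 70% | 20% | 12% |
| 80% | 14.5% | 7.5% |
| 90% | 5% | 2% |

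At f = 50% a normal approximation without continuity correction (SD = √(2·0.25/30) = 0.129) gives 12% for 20 points, which is too low.

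**5. What cannot be computed**

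Step 4 gives how often imbalance occurs, not how far it shifts an estimate. That depends on how strongly wound type predicts volume reduction or closure, and the documents give no figure for this.

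**The case against.** The strongest reply is that the diabetic-foot-ulcer wording is a single sentence and the objectives are written for wounds, so this is mainly a labelling slip. A reader might infer from the mismatch that the trial can conclude nothing about its stated population. The documents do not support that. Randomization protects the comparison in the enrolled mix, and the recorded baseline data allow a diabetic-foot-ulcer subset to be identified.

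A reader might also infer that almost any wound is admitted. That ignores the depth, debridement and perfusion criteria, the exclusions, and recruitment through diabetic foot clinics; the Schedule of Events also places follow-up in a foot wound clinic. The real mix may be mostly diabetic feet. Still, nothing makes it so, and the emergency department is the other main source.

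A third tempting reading is that every efficacy analysis is known to be unadjusted. That goes too far. A multivariable Cox model is planned that can include diabetes, and the volume analysis is unspecified, so its adjustment is unknown. What stands is that the Cox model's stated uses are not the primary comparison, and that the log-rank and non-inferiority comparisons name no covariates.

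Finally, chance imbalance is already allowed for in the type I error of a randomized test, so adjustment serves efficiency and does not rescue validity. That is correct, and the point is put no higher. The trial's role in informing a larger study lowers the immediate stakes.

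**Conclusion.** The concern holds in this limited form. The aim and the entry criteria name different populations and should be reconciled. The comparison is valid for the wounds enrolled; a conclusion confined to diabetic foot ulcers is not supported unless nearly all subjects have one. On the plan's closure rates at two-sided 0.05, power within that subset falls from 78% at a 100% share to 47% at a 50% share. The chance of a gap of 15 points or more between two arms falls from 24.5% to 5% as the assumed share rises from 50% to 90%.

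These figures assume 30 per arm and simple independent allocation, and treat the share as unknown. They do not show that the results will be biased, and they do not size the precision lost. The change is worth making because it is specific and close to free.

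**What to change.** - Keep eligibility as it is. Restate the aim in Study Groups and Design, and the planned conclusions, for the enrolled wound population.
- Define one baseline factor, diabetic foot ulcer versus other, from the recorded wound type, wound location and diabetes history. Fix the derivation rule before outcomes are examined.
- Pre-specify that factor as a covariate in the wound-volume analysis (whose model must be written in any case) and in the non-inferiority analysis, and as a stratum in the log-rank test.
- If most subjects prove to be diabetic, do not add diabetes status as a second covariate; the two would largely overlap.
- Report results in the diabetic-foot-ulcer subset descriptively, with its size by arm.

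Cost: wording and one derived variable. No new data, visits or patients are needed. The downside is that the headline claim is no longer specific to diabetic foot ulcers.

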- Comparison of the following variables between the groups: granulation tissue integrity including hypergranulation state, time to close, flap/graft take, dehiscence, and reoccurrence.

Objective 2

To compare bacterial load, quantitative cultures, and clinical infections in wounds treated with NPWT PRO compared to wounds treated with NPWT PRO with simultaneous irrigation.

H1: Bacterial load measured with quantitative polymerase chain reaction (qPCR) will be progressively lower with continuous irrigation.

H2: Patients treated with simultaneous irrigation and NPWT PRO will have fewer infections defined by qPCR and clinical criteria.

Primary Endpoint:

- Comparison of reduction in bacterial load in wounds treated with NPWT and NPWT with simultaneous irrigation.

Secondary Endpoints:

- Comparison of incidence of infection in wounds treated with NPWT and NPWT with simultaneous irrigation.
- Infection-induced necrosis
- Infection reoccurrence post-closure

Objective 3

Assess changes in molecular markers associated with wound healing and regeneration of healthy tissue.

H1: NPWT PRO with simultaneous Irrigation will improve the levels of growth factors, cytokines, and other molecular markers over NPWT PRO alone.

H2: Negative pressure wound therapy will drive molecular changes in growth factors and other cytokines associated with regeneration of healthy tissue.

Primary Endpoint:

- To compare changes in genes and other molecular markers associated with wound healing between wounds treated with NPWT and NPWT with simultaneous irrigation.

Secondary Endpoint:

- To compare the addition of simultaneous irrigation on gene expression and expression of molecular markers from baseline.

Objective 4

Quality of Life and Patient Satisfaction Analyses

H1: Patients treated with the NPWT PRO device will show greater patient satisfaction with treatment than those treated with KCI Ultra NPWT therapy.

Primary Endpoints:

- To compare Quality of Life and Patient Satisfaction between patients treated with NPWT PRO versus patients treated with KCI Ultra NPWT therapy.
- To compare Quality of Life and Patient Satisfaction between patients with wounds treated with NPWT PRO versus NPWT PRO + SI.
- Evaluate functional status, using the Short Form 36 (SF36). These will be administered at baseline and at the last study visit.

Subjects and Recruitment

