Osteomyelitis will be diagnosed when radiographic and clinical signs are consistent with bone infection. This diagnosis will be confirmed with imaging, bone biopsy, culture or histopathology as most applicable to the individual subject. The bacterial pathogens and sensitivities from bone and soft tissue cultures will be recorded and direct antibiotic therapy applied, if necessary [79].

Study Procedures

Procedures and Evaluations During the Research

The time period from Day 0 to up to 12 weeks will encompass the study therapy administration and evaluation phase. The precise therapy employed will be determined according to subject randomized group allocation, and the duration of the study therapy administration phase will be determined according to individual subject wound healing and status progression and safety evaluations. The study therapy administration phase will comprise the

following progressive activities, as applicable, and will be initiated in the inpatient clinic setting: therapy administration, , and weekly or standard of care wound healing and safety evaluation. The study therapies are delivered in continuous mode throughout the individual subject's entire study therapy administration phase; with the only consistent interruption being for the three times a week wound dressing changes. There will likely be other minimal daily interruptions such as to allow for subject showering and bathing. Therapy administration phase will continue until study wound is ready for closure by secondary intention, after which time the therapy will be discontinued.

Therapy Administration

- Therapy phase to be continued until wound is ready for closure by secondary intention
 - During this therapy administration phase, all subjects will receive NPWT therapy for 4 weeks or until the wound is deemed ready for surgical closure, whichever occurs first. This time point will serve as the individual subject's study evaluation endpoint.
 - Study wound readiness for surgical closure in this study is defined as the time point (evaluation visit) at which the following three factors pertaining to the status of the study wound are determined to co-exist by the study investigator:
 - deep structures (bone, tendon, joint) are covered with granulation tissue
 - the wound depth is < 2 mm
 - the wound bed is ready for skin graft, delayed primary closure or rotational flap to cover the defect.

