 - It is anticipated that most wounds will be determined ready for surgical wound closure by 4 weeks of therapy administration; however this may occur as early as after 2 weeks or subjects may be followed up to the full 12 weeks, and closure may occur anywhere inbetween (to be determined by investigator). It is also possible for some subjects that the wound may not be ready for closure even after 12 weeks. These subjects will be discharged from the study at that time and continue appropriate care for their wound with their physician.
 - The surgical wound closure procedure is performed in the operating room, using the most applicable of the following common mechanisms for closure, as is optimal for the individual subject and wound: delayed primary closure, rotational flap to close the wound, split thickness skin graft.
- Post Wound Closure Evaluation Phase
 - Following surgical closure of the wound, the subject will enter the post wound closure evaluation phase. This phase will last up to week 12 following study enrollment and therapy administration start, such that the duration of the post wound closure evaluation phase will vary for each subject according to the time point at which their wound was deemed ready for surgical closure. For example, a subject whose wound is surgically closed after week 4 of the therapy administration phase will enter a post wound closure evaluation phase that spans from week 5 through week 12, at which time the subject will exit the study. A subject whose wound does not close sufficiently for surgical repair by week 12 will exit the study at that time without entering the post wound closure evaluation phase.
 - The post wound closure evaluation phase will comprise weekly or standard of care evaluations in the outpatient clinic setting. If the wound remains closed with no sign of re-opening or infection, no further efficacy or safety evaluations will be taken at that visit. At post therapy

administration phase completion (as applicable to the individual subject), a standard of care blood draw will again be taken as at the baseline evaluation to assess lab markers.

- If at any of the post wound closure evaluation visits, the wound is found to have re-opened and/or shows signs of infection, the following will occur at the discretion of the physician:
 - Measurements of dehiscence will be taken
 - Surgical debridement of the wound will be done
 - NPWT only will be reapplied per standard of care

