Wound Assessment/ Debridement	X	X	X		X		
Tissue /bone ¹ / wound culture samples for qPCR cultures & bioburden analysis		X	X (Subsequent surgery)				

			while Inpatient)				
NPWT/NWPT (i) randomization/dressing application/changes		X	X	X (Weeks 2-4)	X (Weeks 2-4)		NWPT for maximum 4 weeks after baseline(Day0 surgery) if wound is not closed in the hospital
SF-36 Questionnaire	X					X	
Hyperspectral Imaging Analysis	X						To occur prior to surgery
Discharge Instructions			X		X		
Offloading			X	X	X		At hospital discharge & continuing to Week 12
Adverse Events		X	X	X	X	X	
Current/concomitant antibiotics	X	X	X	X	X	X	
Wound imaging/measurement		X	X		X	X	While active study wound is present
Neuropathy Disability Score in Patients with Diabetes	X						

¹ Only if performed as a necessary part of standard of care.

² Subjects who heal before week 12 will exit the study and complete EOS visit.

Biostatistics

Sample Size Justification:

There are no published data with the Cardinal PRO negative pressure wound therapy (NPWT) device with or without irrigation in order to determine an estimate of the sample size for this study. One of the purposes of this project is to obtain data, so we can power a larger multicenter study. Even though the KCI NPWT device with irrigation has been commercially available, there is little data about volume change or wound healing in the population we are studying.

The previous sample size justification was based on a comparison of the proportion of wounds expected to achieve surgical closure. The proportion of subjects with closed wound was 62% using traditional KCI NPWT and 94% using NPWT with periodic irrigations with Prontosan. For the sample size, we estimated 85-90% wound closure with NPWT with irrigation and 60% wound closure with NPWT without irrigation. We assume the NPWT devices (KCI and Cardinal) without irrigation would have similar results.

Equations

The following formula was used to estimate the required sample size, n , for the relative difference in proportions P_1 and P_2 .

$$n = \frac{\left(Z_{\alpha/2} \sqrt{2P(1-P)} + Z_{\beta} \sqrt{P_1(1-P_1) + P_2(1-P_2)} \right)^2}{(P_1 - P_2)^2}$$

where

$$P = \frac{P_1 + P_2}{2}$$

Using the formula above and assuming 90% wound closure with NPWT with irrigation and 60% wound closure with NPWT without irrigation and a type I error of 0.1, the required sample size is about 25. If a Type I error of 0.05 is assumed, then the required sample size is about 31.

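### One listed primary outcome counts only secondary-intention closure, while the plan closes ready wounds surgically and never says how surgical closure enters the time-to-event analysis

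*Combined protocol and SAP*

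**What the plan says.** **Outcome.** Study Groups and Design lists three primary outcomes: "Primary outcomes will include rates of wound healing, time to closure by secondary intention, and recurrence rate".

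**Objectives.** Study Objectives and Endpoints ranks them differently. For the irrigation comparison it gives "Primary Endpoint: Comparison of reduction in wound volume between wounds treated with NPWT PRO and NPWT PRO with simultaneous irrigation", and wound volume is also primary for the device comparison. Time to close appears among the secondary endpoints with no mode of closure: "granulation tissue integrity including hypergranulation state, time to close, flap/graft take, dehiscence, and reoccurrence".

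**End of therapy.** Therapy Administration opens with "Therapy phase to be continued until wound is ready for closure by secondary intention". The next item says "all subjects will receive NPWT therapy for 4 weeks or until the wound is deemed ready for surgical closure, whichever occurs first". One of the three readiness criteria is that "the wound bed is ready for skin graft, delayed primary closure or rotational flap to cover the defect".

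**Closure.** The same section continues: "The surgical wound closure procedure is performed in the operating room, using the most applicable of the following common mechanisms for closure". The mechanisms listed are delayed primary closure, rotational flap and split-thickness skin graft. Most wounds are expected to be ready by 4 weeks. Closed subjects then move to a post-closure phase that lasts to week 12.

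**Sample size.** "The previous sample size justification was based on a comparison of the proportion of wounds expected to achieve surgical closure". The calculation that follows uses 60% closure without irrigation and 85-90% with it.

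**Analysis.** Survival Analyses Models makes Kaplan-Meier with a log-rank test the primary method and refers to full (100%) closure. It gives neither the mode of closure nor a rule for surgical closure.

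**The concern.** Secondary intention normally means that a wound is left to heal without surgical closure. The protocol makes the same distinction: its description of the home control device separates secondary from tertiary (delayed primary) intention. A wound that goes to graft, flap or delayed primary closure therefore does not have the event named in the design paragraph, at least not before that surgery. Surgical closure is nevertheless the route to success that the plan expects for most wounds, and it is the quantity on which the trial was sized.

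Two things are at stake. First, an analyst who follows the design paragraph as written would not count the expected successes. Second, one who follows Survival Analyses Models would have to choose whether surgical closure is an event, a censoring or a competing event. These choices can give opposite impressions of the same data. The investigator judges readiness in an open-label trial, so under the literal reading an unblinded decision would also determine who leaves the risk set.

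**Working it through.** **1. Reproduce the plan's own figure.** Inputs from Sample Size Justification: P1 = 0.60, P2 = 0.90, power 0.80, two-sided alpha 0.10 or 0.05. With the printed formula, P = 0.75, √(2 × 0.75 × 0.25) = 0.612 and √(0.24 + 0.09) = 0.574.
- Alpha 0.10: (1.645 × 0.612 + 0.842 × 0.574)² / 0.30² = 24.69, so 25 (plan: about 25).
- Alpha 0.05: (1.960 × 0.612 + 0.842 × 0.574)² / 0.30² = 31.50, so 32 (plan: about 31).

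The closure rates are therefore read as the plan used them. Enrolment is 90 at 1:1:1, so 30 per arm.

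**2. Ceiling on the literal event.** Read the planning rates as surgical closure. Subjects who could close by secondary intention without prior surgical closure number at most 30 × (1 − surgical closure rate).

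| Surgical closure, without / with irrigation | Without | With |
|---|---|---|
| 60% / 90% | 30 × 0.40 = 12 | 30 × 0.10 = 3 |
| 60% / 85% | 12 | 30 × 0.15 = 4.5 |

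**3. Effect of the definition on crude counts.** Let q be the share of the remaining wounds that close without surgery. The documents give no value for q, so a range is shown at 60% / 90%, with q equal in both arms.

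| q (assumed) | Secondary-intention closures, without / with | Closures by any method, without / with |
|---|---|---|
| 0.25 | 3.0 / 0.75 | 21.0 / 27.75 |
| 0.50 | 6.0 / 1.5 | 24.0 / 28.5 |
| 1.00 | 12 / 3 | 30 / 30 |

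At q = 0.50, for example, closures by any method are 30 × (0.60 + 0.40 × 0.50) = 24.0 and 30 × (0.90 + 0.10 × 0.50) = 28.5. The literal count favours the arm without irrigation. The any-method count favours irrigation, or is equal at q = 1. For the literal count to favour irrigation, q would have to be more than 0.40/0.10 = 4 times as high with irrigation (0.40/0.15 = 2.7 times at 85%).

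**4. Kaplan-Meier with surgical closure censored.** Assume constant weekly hazards over 12 weeks, s for surgical closure and h for secondary-intention closure.
- Crude incidence = h/(s + h) × (1 − exp(−12(s + h))).
- Censored Kaplan-Meier estimate = 1 − exp(−12h).

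Surgical closure is held at 60% and 90% by solving for s. The value h = 0.01 without irrigation is an assumption.

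| h with irrigation | Crude incidence, without / with | Censored Kaplan-Meier, without / with |
|---|---|---|
| 0.01 (equal) | 7.2% / 4.0% | 11.3% / 11.3% |
| 0.02 (doubled) | 7.2% / 6.8% | 11.3% / 21.3% |
| 0.03 (tripled) | 7.2% / 8.5% | 11.3% / 30.2% |

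With h = 0.02 without irrigation, equal hazards give a crude 13.3% / 6.8% and a Kaplan-Meier estimate of 21.3% in both arms.

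The equal-hazard row shows the risk. Surgical closure differs by 90% − 60% = 30 percentage points, and the censored analysis shows no difference. The other rows show that the direction of that analysis depends on hazards the plan does not give.

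**The case against.** The strongest reply is that the phrase is a slip. The first line under Therapy Administration uses secondary intention for a milestone that the following lines define as readiness for surgical closure, so the authors may mean one thing by both. If full closure in Survival Analyses Models includes surgical closure, the problem disappears. This reading is plausible, but the documents do not confirm it, and the phrase stands in a list of primary outcomes. An analyst needs the rule in writing.

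Three stronger readings are tempting, and the documents do not support them.
- A reader might infer that this is the trial's primary outcome. It is one of three in a narrative sentence, and the objectives name wound-volume reduction as primary.
- A reader might infer that the plan censors surgical closures. It does not say so; it is silent.
- A reader might infer that the better arm must show fewer events and that the log-rank result would reverse. The log-rank test compares hazards among those at risk, and step 4 shows equal or favourable curves for irrigation. Even crude counts need not reverse.

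Two smaller objections also stand. A wound that re-opens after surgery may re-enter therapy and could later close without surgery, so the ceiling covers only closure without prior surgical closure. The plan also calls its surgical-closure sample size the previous justification, so treating 60% and 85-90% as surgical rates is a reading, though no other calculation replaces it.

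**Conclusion.** The point holds as a conflict between a named outcome and the planned route to closure, combined with a missing rule for surgical closure. Read literally, the outcome can occur without prior surgical closure in at most 12 of 30 subjects without irrigation and 3 of 30 with it (4.5 at 85%). These are ceilings on crude events, not expected counts. They rest on equal arms of 30 and on the planning rates being surgical closure rates.

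Under that reading crude counts could favour the arm with fewer surgical closures. A log-rank test with surgical closures censored would have few events and informative censoring, and could hide a surgical-closure benefit. Its direction cannot be settled from the documents, because q and the hazards used above are illustrative. The outcome's rank is a second inconsistency: primary in the design paragraph, secondary in the objectives. Both should be settled before any closure analysis is run, because the definition decides which subjects count as successes.

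**What to change.** 1. In Study Groups and Design and in Survival Analyses Models, define the time-to-event outcome as time to wound closure by any method. Count surgical closure as an event and record the method of closure.
2. If secondary-intention closure is kept, report it descriptively by cumulative incidence, with surgical closure as a competing event.
3. State whether time to closure is primary or secondary, and make the design paragraph agree with Study Objectives and Endpoints.
4. The two end-of-therapy wordings under Therapy Administration, closure by secondary intention and surgical closure, contradict each other. The sponsor must reconcile them; no clinical rule is proposed here.

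The cost is protocol and analysis-plan wording. No new visits or measurements are needed, because the date and mechanism of a surgical closure arise from the study procedure itself.
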